- ED must plan to admit patient to the hospital or Clinical Decision Unit.

Exclusion criteria:

- Adults unable to consent
- Individuals who are not yet adults (infants, children, teenagers)
- Pregnant women
- Prisoners
- Prior history of gastroparesis
- Prior history of gastric, or small bowel surgery
- Prior history of inflammatory bowel disease
- Concern for infectious colitis
- Non-English speaking
- Evidence of dysphagia at the time of presentation
- Presence of bright red blood per rectum
- Allergy to metoclopramide or erythromycin
- Code status of DNR/DNI or CMO
- Prior history of abdominal radiation
- Presence of ICD or pacemaker or other implanted electronic devices
- Abdominal pain suggesting an acute abdomen or obstruction. In clinical practice, only patients with crampy abdominal pain due to

INVESTIGATOR STUDY PLAN - REQUIRED

Crohn's disease, previous intestinal surgery and a previous history of radiation therapy require a patency capsule or CT enterography before capsule endoscopy.

- Patients who cannot undergo surgery

6) Study-Wide Number of Subjects*

Not applicable – not a multi-site study

7) Study-Wide Recruitment Methods*

Not applicable – not a multi-site study

8) Study Timelines*

1. The participation of individual subjects in this study will be approximately 31-40 days (the length of their hospitalization plus an additional thirty days for follow up).
2. The duration anticipated to enroll all study subjects is about 24 months.
3. The estimated date for the investigators to complete this study and data analysis is two years.

9) Study Endpoints*

The primary endpoint will be time to diagnosis. Secondary endpoints will include hospital length of stay, number of invasive procedures, blood product transfusions.

10) Procedures Involved*

Screening

Patients presenting to the Emergency Room with NHGIB (defined as melena or hematochezia) will be identified by a member of the ED staff.

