- Data analysis plan: As discussed above, data will be obtained through review of medical records. Specifically we will be looking at time to diagnosis of bleeding source, laboratory values, number of blood products transfused procedures performed, along with additional measures as described above. Once we have separated our two cohorts we will perform chi-square and standard t-tests to compare the different dependent variables in the two cohorts. We will also perform Kaplan-Meier curve analyses to compare length of stays and time to diagnosis which is the primary metric of this study.
- Steps that will be taken to secure data: All clinical data from individual subjects will be de-identified and given a study number. The study number will serve as a link between the data and the subject's identifiable information. RedCAP online encrypted database will be used to store the dataset. The database will only be accessed by the primary investigator and research assistants.
- Data will be exported for analysis as a de-identified data set. The de-identified dataset (which would be absent of any PHI) would be transferred in a password-encrypted email to the external sponsor.
- The external sponsor – Olympus Medical Systems – will have access only to the de-identified data set and will not have access to the study key with identifying health information.
- Identifier keys will be destroyed once primary data analysis is complete.
- No identifying information will be used in any report or publication generated from this study.
- Power analysis: Based on a previous retrospective epidemiology study, the average time to diagnosis for subjects presenting with non-hematemesis GI bleeding (NHGIB) who underwent a conventional workup was 30 hours (standard deviation of 6.1). Subjects with NHGIB who had an early capsule as the first diagnostic test had an average time to diagnosis of 15.9 hours (standard deviation of 12.2). This calculates an effect size of 1.49301. This is

INVESTIGATOR STUDY PLAN - REQUIRED

an effect we are looking to replicate prospectively in this study. Using this data with an assumed α of 0.05 and using a sample size of 80 subjects in the early capsule deployment group and 80 subjects in the Conventional Workup group the calculated power is 99%.

13) Provisions to Monitor the Data to Ensure the Safety of Subjects*

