PUBLISH DATE JUNE 20, 2018

STATISTICAL ANALYSIS PLAN

TITLE: A comparison of early deployment of a video capsule (Endocapsule EC-10: Olympus Tokyo. Japan) in the Emergency Department versus conventional work-up of non-hematemesis gastrointestinal bleeding [NHGIB].

NCT02442830

[name], PHD, PRINCIPAL INVESTIGATOR

STATISTICAL ANALYSIS PLAN

Study outcomes:

The primary outcome for this study was the rate of localization of bleeding during hospitalization. Localization of bleeding was defined as identification of blood or identification of a lesion with high-risk stigmata of recent hemorrhage (SRH). Secondary outcomes included, overall rate of localization of bleeding by the end of admission, anatomic location of bleeding or the bleeding source, rate of endoscopic therapy, rate of readmission, rate of diagnosis of vascular lesions (defined as Dieulafoy's lesions or angioectasias), rate of re-bleeding within 30 days of discharge, rate of all-cause mortality within 30 days of hospitalization, cumulative direct hospital costs by the end of admission, and overall rate of identifying the etiologic diagnosis.

Sample size calculation:

The study was planned as a superiority trial and the estimated probability of localization of bleeding during hospitalization in the Early Capsule arm to be two times greater than that of the Standard of Care arm (i.e. estimated hazard ratio of 2.00). We found no prior studies similar to our methodology, so prior experience at our institution guided the estimation of effect. Power analysis revealed that for this effect size to be detected (80% chance) as significant at the 5% level, a sample of at least 72 patients (36 per group) would be required.

Statistical analysis:

Patient characteristics were described as means with standard deviation (SD) or as proportions. Time to localization and time to first procedure were described using medians with interquartile range (IQR). Hospital costs were described in US dollars (USD).

Independent variables selected for analysis included those previously suggested as prognostic indices for NHGIB. Variables chosen for analysis included gender, race, age, vital signs at admission, use of anticoagulants, use of non-steroidal anti-inflammatory drugs (e.g. aspirin and ibuprofen; NSAIDs), use of a P2Y₁₂ inhibitor (e.g. clopidogrel), factors that contribute to the Glasgow-Blatchford Score, and type of bleeding at admission (i.e. hematochezia, melena, or symptomatic anemia).

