Univariate analyses involved Wilcoxon-Rank sum tests for continuous variables and Chi-square or Fisher's Exact tests for binary variables. A Kaplan-Meier survival analysis with a Log-rank test compared the cumulative incidence of endoscopic localization of bleeding for the two groups. For multivariate analyses, independent variables with a difference at $p<0.10$ following univariate analysis or those noted to be unevenly distributed between the two cohorts were included as covariates. A p -value of less than 0.05 was significant. Statistical analysis was performed using STATA 13.

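### The SAP gives a median and IQR for time to localization without defining the patient set; read plainly, they describe only localized patients, a group selected by the primary outcome.

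*SAP*

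**What the plan says.** The SAP's Statistical analysis section opens with descriptive conventions: means with SD or proportions for patient characteristics, US dollars for costs, and between them "Time to localization and time to first procedure were described using medians with interquartile range (IQR". No patient set is named, and there is no rule for a patient discharged without localization.

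Under Study outcomes the SAP states: "The primary outcome for this study was the rate of localization of bleeding during hospitalization". Time to localization is not among the listed secondary outcomes. The protocol differs. Section 9 reads "The primary endpoint will be time to diagnosis", and section 10 (Review and Follow-Up) measures that time from ED entry to localization of the bleeding source. So the SAP's time to localization is, in substance, the protocol's primary endpoint. For its analysis, protocol section 12 lists chi-square and t-tests and adds: "We will also perform Kaplan-Meier curve analyses to compare length of stays and time to diagnosis which is the primary metric of this study".

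The SAP's comparison over time is "A Kaplan-Meier survival analysis with a Log-rank test compared the cumulative incidence of endoscopic localization of bleeding for the two groups". It gives no censoring rule and does not say that quantiles will be read from the curve. A separate sentence reads "Univariate analyses involved Wilcoxon-Rank sum tests for continuous variables and Chi-square or Fisher's Exact tests for binary variables"; it follows a list of independent variables and leads into covariate selection.

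**The concern.** A patient who is never localized has no raw time to localization. A plain median and IQR therefore leave that patient out. The trial is built on the expectation that localization differs between the arms, so the patients left out would differ in number, and probably in kind, from one arm to the other. Randomisation does not make the remaining subsets comparable.

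At stake is the figure that readers are most likely to repeat: hours to localization in each arm. The log-rank test gives a p-value and the rate gives a proportion, but the median and IQR are the only stated summary in hours. If they come from localized patients alone, they can give a different picture from the curve they accompany.

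**Working it through.** **1. The plan's own figure.** Inputs from the SAP, Sample size calculation: "i.e. estimated hazard ratio of 2.00", 80% power, 5% level (two-sided assumed, since sidedness is not stated), 36 per group. Freedman's formula gives

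D = (z₀.₉₇₅ + z₀.₈₀)² × [(HR + 1)/(HR − 1)]² = 7.849 × (3/1)² = 70.6, so 71 events, or 72 with equal arms.

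The 72 is reproduced, with patients equated to events, that is, with every patient localized. (Schoenfeld's formula gives 66.) For this point it confirms only that HR 2.00 is the planning premise.

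**2. Are non-localized patients expected?** Yes. Protocol section 10 (Procedure) provides for a non-diagnostic capsule study followed by observation and possible discharge. Protocol section 4 reports earlier diagnostic yields of 72.2% (26/36) for capsule, 52.9% for upper endoscopy and 47% for colonoscopy. These are yields per procedure, not per work-up, so they do not supply the localization share in either arm.

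**3. Raw times or Kaplan-Meier quantiles?** The sentence stands among plain descriptives and treats time to first procedure in the same words. The Kaplan-Meier sentence comes later and mentions no quantiles. Raw values are the more natural reading.

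The planning premise points the same way. The SAP plans for a localization probability in the early arm twice that in the Standard of Care arm. Taken literally, 2 × p(SOC) ≤ 1, so p(SOC) ≤ 50%. An all-patient upper quartile needs 75% localized. With non-localized patients counted as such, that arm has no upper quartile, and below 50% it has no median. A complete IQR there would have to come from localized patients only, or from censoring at discharge, a rule the SAP does not give. If only the hazard ratio is used, the 75% requirement for the upper quartile remains.

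**4. Size, under assumptions.** Assume exponential times, HR 2.00, a common follow-up T, and p(SOC) = 50%. With hazard λ in the Standard of Care arm:

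- λT = −ln(0.50) = 0.693; p(early) = 1 − exp(−2 × 0.693) = 75%.
- All-patient medians: 0.693/λ (conventional) and 0.693/(2λ) (early). Ratio 0.50.
- Localized-only medians fall where half of each arm's localized share has been reached. Conventional, at 25%: −ln(0.75)/λ = 0.288/λ. Early, at 37.5%: −ln(0.625)/(2λ) = 0.235/λ. Ratio 0.235/0.288 = 0.82.
- With 36 per arm, 18 and 27 patients are localized, so the raw medians leave out 18 conventional and 9 early patients.

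**5. Range over the assumed Standard of Care share.**

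| Localized, SOC | Localized, early | Ratio, localized only | Ratio, all patients |
|---|---|---|---|
| 30% | 51% | 0.91 | SOC median not reached |
| 40% | 64% | 0.86 | SOC median not reached |
| 50% | 75% | 0.82 | 0.50 |
| 60% | 84% | 0.76 | 0.50 |
| 70% | 91% | 0.70 | 0.50 |
| 80% | 96% | 0.64 | 0.50 |
| 90% | 99% | 0.57 | 0.50 |

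In this model selection always pulls the ratio toward 1, and more so as fewer patients are localized.

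**The case against.** The strongest reply is that the sentence only describes. The stated between-arm analysis is Kaplan-Meier with a log-rank test, which can keep non-localized patients in the risk set, and medians and quartiles can be read from that curve for all patients wherever it reaches them. In the SAP, time to localization is neither primary nor a listed secondary outcome.

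Most of this stands. The text does not exclude Kaplan-Meier quantiles, and no descriptive median can alter the log-rank result or the primary rate. But the SAP does not say that quantiles come from the curve, and medians printed side by side are read as a comparison whatever the verb.

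Three stronger readings are tempting, and the documents do not support them:

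- *That the SAP tests the arms within localized subsets.* It names no such test.
- *That a Wilcoxon test is run on these times.* The Wilcoxon sentence most naturally covers the independent variables listed just before it. Time to localization is neither assigned to it nor excluded.
- *That the early arm would look slower.* This can be constructed: half of each arm localized at a median of 18 h, and a further 25% localized only in the early arm at a median of 45 h, gives localized-only medians of about 18 h (conventional) and 24.5 h (early). But those inputs are not in the documents, and the scenario lets the capsule speed up no diagnosis. Its cumulative hazard ratio is about 1.10 at 24 h and 1.47 at 48 h, against the planned 2.00. Scaling the early-arm times by the protocol's own ratio (15.9/30 = 0.53, section 12) gives about 12.9 h against 18 h, with no reversal.

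**Conclusion.** The point holds as a defect in how time to localization is summarised. The patient set is undefined. On the plain reading, the only stated summary in hours of the protocol's primary metric is confined to patients selected by the SAP's primary outcome. This is more than a missing detail, because a better summary is available from the same data.

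The direction and size in the real data cannot be known from the documents. Under exponential times, HR 2.00 and 50% against 75% localized, a halving of the median (0.50) would appear as 0.82. Across assumed Standard of Care localization of 30% to 90%, the localized-only ratio runs from 0.91 to 0.57. These figures rest on the assumed distribution, the common follow-up and the assumed shares. The conclusion about the patient set does not.

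**What to change.** Replace the sentence on time to localization with a rule along these lines:

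- Summarise it over all randomised patients by arm, counting those discharged without localization as not localized.
- Report the median and quartiles from the cumulative incidence curve, entering 'not reached' where that applies.
- Add the proportion localized by fixed times (for example 24 h and 48 h) and by discharge.
- If a median among localized patients is also shown, give its denominator, label it descriptive and not for between-arm comparison, and state that no Wilcoxon test is run on it.

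The cost is SAP wording and a few table rows. The protocol already collects procedure times, time to diagnosis and time of discharge (section 10, Review and Follow-Up). The downside is small: the upper quartile, and possibly the median, may be 'not reached' in one arm, and the fixed-time proportions then carry the description.

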In patients with hematemesis, upper endoscopy remains the diagnostic and therapeutic modality of choice. However patients with melena and hematochezia may benefit from early VCE since both signs and symptoms provide poor localization as to the origin of bleeding. Data from our previous study suggests that the ingestion of a video capsule in the emergency department could quickly and non-invasively provide clinicians accurate data as to the origin of the bleeding. This information could provide a guide to further management of the patient. Video capsule endoscopy is able to visualize bleeding in the esophagus, stomach, duodenum, small intestine and right colon, thereby eliminating the guess work of deciding which endoscopic approach to use.

At UMass, we have shown that of the 36 patients who received a video capsule, 26 (72.2%) had diagnostic studies (i.e. bleeding was identified). In comparison, 152 patients required upper endoscopy (of which 52.9% were diagnostic) and 64 patients required colonoscopy (of which 47%

INVESTIGATOR STUDY PLAN - REQUIRED

were diagnostic). Of those 26 patients with diagnostic capsule studies, 13 also required upper endoscopy, 1 required a colonoscopy, and 4 required both a colonoscopy and endoscopy. It is important to recognize, however, that often capsule studies are performed AFTER upper endoscopy and colonoscopy and performed and are negative. This sequence is the conventional work up of bleeding. Despite being performed later in the hospital course of our patients, capsule studies have a high diagnostic yield. In reality VCE is used uncommonly in acute bleeding because it is rarely considered in the context of acute GI bleeding

In this study, we propose the approach of using the video capsule as the first diagnostic test PRIOR to colonoscopy and endoscopy; this may lead to a shortened time to diagnosis, a reduction in length of stay, and a reduction in numbers of procedures due to early, accurate localization of the source of bleeding. All of these components could result in better quality of care and cost containment.^{1,2} Further, it is known that 80% of patients stop bleeding spontaneously. Thus the earlier they are examined the more likely the origin of the bleeding is likely to be found

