During hospitalization, data will be recorded from ED pulse check, Meditech, Soarian, and Allscripts regarding fluid administration, transfusion of pRBC, initial hematocrit, times and types of procedures (e.g. upper endoscopy, enteroscopy, colonoscopy), time from entry to ED to time to diagnosis (i.e. localization of source of bleeding), admission disposition (i.e. clinical decision unit, regular floor, ICU), time of discharge. The procedures involved in the hospitalization (i.e. upper endoscopy, enteroscopy, and colonoscopy) will be done as part of standard of care. All of this information will be linked to the subject’s study ID number as described above. This data collection is for research purposes only.

In addition, the costs of the procedures will be collected through financial services. The costs that will be collected are both the fixed and variable costs associated with each patient in the study. We will also collect the direct and indirect costs allocated to each patient. All charges associated with the admission for each patient in the study will have costs allocated. This will be evaluated as an additional data point to compare the two arms of the study. No additional PHI will be collected.

Telephone Follow-Up

Subjects will also be contacted by phone by a research staff member at two different time points following their discharge from the hospital. These time points will be at 3 days (+2 days) and 30 days (+/- 3 days) following their discharge. At these time points a staff member will call a subject to obtain information about whether or not a patient has had recurrent bleeding and whether or not the patient had to be readmitted to a hospital or emergency room for

INVESTIGATOR STUDY PLAN - REQUIRED

recurrent bleeding. Please see attached form for telephone script that staff member will read along with particular questions that will be asked.

No more than three attempts will be made at each time point to reach the subject. If a message is left, it will be "Hello, this is [name] calling from UMass looking to speak with [subject]. Please call back at [number] at your earliest convenience. Thank you."

11) Data and Specimen Banking*

N/A – no data banking.

12) Data Management*

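### The SAP compares the cumulative incidence of in-hospital localization by Kaplan-Meier and log-rank but gives no rule for patients who leave or die without localization, and does not say whether the target is the proportion localized or the speed

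*SAP*

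**What the plan says.** SAP, Study outcomes: the primary outcome is the rate of localization within the hospital stay, so each patient's window closes at that patient's own discharge or death. A secondary outcome is the "overall rate of localization of bleeding by the end of admission".

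SAP, Sample size calculation: the probability of localization is taken "in the Early Capsule arm to be two times greater than that of the Standard of Care arm (i.e. estimated hazard ratio of 2.00"), and "a sample of at least 72 patients (36 per group) would be required".

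SAP, Statistical analysis: "A Kaplan-Meier survival analysis with a Log-rank test compared the cumulative incidence of endoscopic localization of bleeding for the two groups". The same section names chi-square or Fisher's "Exact tests for binary variables", as part of the univariate analyses and without tying them to the primary outcome.

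Protocol section 10 (Review and Follow-Up) records "time from entry to ED to time to diagnosis (i.e. localization of source of bleeding") and the time of discharge. The SAP does not adopt ED entry as time zero. Protocol section 12 also plans Kaplan-Meier curves for time to diagnosis. Neither document gives a censoring rule, a horizon, or a way to handle a patient who leaves or dies with no source found.

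**The concern.** Discharge without localization is not ordinary censoring. For an outcome confined to the hospital stay, it ends the possibility of the event. Censoring there makes the Kaplan-Meier curve describe what would have happened had those patients stayed and gone on being localized at the same rate as the others. That is not the cumulative incidence the SAP names.

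The documents foresee such patients and describe different routes out of hospital. Under Protocol section 10, capsule patients with no blood seen and no ongoing hematochezia go to observation for up to 23 hours and are assessed for discharge. Conventional patients leave on the hospitalist's recommendation after treatment. Protocol section 15 hypothesizes a shorter stay in the early capsule group. Non-localized patients are unlikely to be rare: Protocol section 4 reports that "of the 36 patients who received a video capsule, 26 (72.2%) had diagnostic studies", with 52.9% for upper endoscopy and 47% for colonoscopy (yields per procedure, not per patient).

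The target is also unclear. Rate, probability and cumulative incidence point to a proportion; a hazard ratio points to speed. If the log-rank and the simple proportion disagree, the plan does not say which decides, and the choice could follow the data.

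**Working it through.** **1. The plan's own figure.** Freedman's formula for a hazard ratio of 2.00, 80% power and a two-sided 5% level (sidedness assumed) gives events = (1.960 + 0.842)² × [(2 + 1)/(2 − 1)]² = 7.849 × 9 = 70.6. That is 36 per arm, or 72, if every patient is localized. Schoenfeld's formula gives 65.3. The match suggests that the log-rank was the test in mind and that no allowance was made for patients who are never localized.

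**2. A doubled probability is not a hazard ratio of 2.00.** Under proportional subdistribution hazards, 30% v 60% localized corresponds to ln(0.40)/ln(0.70) = 2.57. Conversely, a ratio of 2.00 applied to 30% gives 1 − 0.70² = 51%, not 60%.

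**3. The curve.** Assume constant hazards, half of patients eventually localized, and a mean time to exit of 48 h. Each cause-specific hazard is then 1/96 per hour. At 72 h:
- one minus Kaplan-Meier, censored at discharge: 1 − exp(−72/96) = 0.53
- true cumulative incidence: 0.5 × [1 − exp(−72/48)] = 0.39

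The gap depends on timing. The next figures assume lognormal times, 60% localized, and log-SD 0.4 for discharge of non-localized patients. With the power analysis's early capsule timing (it says the group "had an average time to diagnosis of 15.9 hours (standard deviation of 12.2"), which as a lognormal has median 12.6 h and log-SD 0.68, the 72 h curve reads 68% against a true 60% if median discharge is 39 h, and 65% if it is 45 h. With the conventional timing (mean 30 h, SD 6.1) it reads 61% against 60% for discharge at 72 h, and 66% for discharge at 48 h.

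**4. The test, read as a test of the proportion.** Simulated at 36 per arm, 6,000 trials per scenario. Both arms have 60% localized with equal timing (lognormal, median 24 h, log-SD 0.6, unless stated). Non-localized patients are censored at discharge. All discharge times are assumptions. The 39 h adds the pilot's 4 h mean to capsule, upper limits of 8 h recording and 4 h reading, and 23 h observation (Protocol section 10). The 72 h has no source in the documents.

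| Median discharge of non-localized patients, capsule v conventional | Log-rank rejection |
|---|---|
| 72 v 72 h, or 48 v 48 h | about 5% |
| 48 v 72 h | about 8% |
| 39 v 72 h | about 12%, nearly all favouring capsule |
| 72 v 48 h | 7–8%, nearly all favouring conventional |
| 39 v 72 h, power-analysis capsule timing in both arms | 5–6% |
| 39 v 72 h, 80% localized | 9–10% |
| 39 v 72 h, 90% localized | about 7% |

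In the 39 v 72 h case with 60% localized, the log-rank is significant and the chi-square is not in about 10% of trials. Under equal timing, chi-square stays near 5%.

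**5. The target decides the answer.** Give both arms the same cause-specific hazard (mean 40 h) with discharge at 39 v 72 h. The censored log-rank then rejects 5.0%, as it should. Keeping non-localized patients at risk rejects 23%, because the proportions truly differ (62% v 82%).

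Now set 60% localized in both arms, with the power analysis's timing in each (15.9 v 30 h). The kept-at-risk test, which is what Gray's test amounts to here, rejects about 21%, nearly all favouring capsule. Chi-square rejects 5%.

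**The case against.** The strongest reply is that the primary may be about speed. The end-of-admission proportion is listed separately as secondary, and the hazard ratio, the log-rank and the Protocol's time to diagnosis all fit a speed target. For that target a log-rank censored at discharge is valid. This stands. What it does not cure is the label on the curve, or an outcome worded as a rate and a probability.

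Censoring at discharge is also an assumption: the SAP neither states nor excludes it. If non-localized patients stay in the risk set to a common horizon, with no other censoring, the curve is a true cumulative incidence. That stands too, and is a reason to write the rule down.

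The 12% case is strained. Its 39 h rests on a capsule read by 16 h (4 + 8 + 4), yet with a 24 h median about 75% of localizations fall after 16 h and 21% after 39 h. With the power analysis's capsule timing only about 5% fall after 39 h, and the lean nearly vanishes. The 60% is also weakly grounded, since several tests per patient could raise the per-patient share.

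Finally, the binary tests are already in the SAP, so an artefact would show beside them. True, but the SAP does not say which result decides.

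A reader might infer that the log-rank is invalid, or that this trial's error rate is inflated in favour of the capsule. The documents do not support either. They give no discharge times, the direction reverses if conventional negatives leave first, and the test is sound for the cause-specific hazard.

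**Conclusion.** The point holds as an omission in the primary comparison. The SAP names a cumulative incidence and gives no rule for patients whose window closes without the event. If they are censored at discharge, its estimator does not estimate that quantity. It also equates a doubled probability with a hazard ratio of 2.00, although 30% v 60% corresponds to 2.57.

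The effect on the test is conditional. It arises only if patients are censored at discharge, if non-localized patients leave at different times in the two arms, and if the result is read as a comparison of proportions. Rejection of about 5% to 12% at an equal 60% localized is illustrative: the top of that range is an unfavourable assumption, and it falls as more patients are localized. Confidence is high for the missing rule and the mislabelled curve, and moderate for the consequence. It should be fixed because it concerns the primary comparison and the remedy is cheap.

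**What to change.** In the SAP:

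- Name the target and time zero, for example the ED entry time the Protocol already records.
- Treat discharge or death without localization as a competing event, and show Aalen-Johansen curves in place of one minus Kaplan-Meier.
- If the target is the proportion localized in hospital, make the chi-square or Fisher's test already named, on all randomized patients, the deciding comparison.
- If the target includes speed, use Gray's test or a cause-specific log-rank and label it as such. Note that Gray's test also responds to timing, so it is not a test of the proportion alone.
- State in advance which comparison is primary.

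The cost is a few sentences and slightly more analysis; discharge times are already collected. Little or no power was lost in the cases tried. At 30% v 60% localized and 36 per arm, keeping patients at risk gives 73% against 69% for the censored log-rank with 48 h discharge in both arms, and 72% against 71% with 72 h. The downside is an effect measure that is less familiar and does not match the sizing hazard ratio of 2.00 exactly.
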